1.1.12 Breast cancer risk communication in MyPeBS

Refs: 3,13,14,40,55,90,130

A major issue is to make women better informed and more active in their screening decisions, as clearly acknowledged by several international studies. Indeed a key concern of national screening programs in all participating countries is to promote informed choices about decisions to attend screening, and any subsequent treatment options. Informed choices require good quality relevant information to be communicated to women, to allow them to make decisions consistent with their values.

This is in line with the ethical principle of autonomy, which requires that physicians and other healthcare professionals should allow women to participate to informed decision-making concerning their healthcare choices, especially for preventive care decisions. Furthermore, a balanced consideration of any screening

program should consider the harms of that program as well as benefits (beneficence and non-maleficence). Amongst the potential harms of risk-stratified screening are undue increases in general anxiety or distress related to cancer.

Communication of cancer risk estimations to individuals has been largely developed over the past 20 years for use in patients bearing a genetic high-risk predisposition to cancer. Communication of cancer risk as a way to target preventive interventions has recently been extended to the general population, with positive results. Tools are ready that allow effective communication of risk evaluations, together with prevention proposals, to individuals in the community (Lerman, Martinez-Alonso, O'Donnell, Fox, Morman, Johannsson, Wardle).

MyPeBS trial has the overall aim of assessing the impact of risk-stratified screening on women's understanding, awareness and emotional responses as compared to standard of care. Indeed, in the context of breast cancer screening, the psychological impact of risk communication needs to be further analyzed and all adverse reactions need to be anticipated. We will assess women's risk perception, anxiety, comprehension of the information provided, satisfaction, participation to the decision-making process, and quality of life in both arms, throughout the MyPeBS clinical trial.

It has been shown that attendance to the screening programs is related to individuals' socioeconomic profiles. Notably, underserved populations remain those where screening is lower and BC is discovered in more advanced stages with higher mortality. We will assess the attendance to MyPeBS clinical trial according to socio-economic variables. It will also be important to interpret results regarding understanding and anxiety with regards to these socioeconomic variables. The final recommendations to be produced upon MyPeBS results shall also address specific issues regarding equity of the program and access for underserved women.

Of note, the teams involved in MyPeBS have previous experience with breast cancer risk communication in the general population:

Manchester's team conducted the Predicting Risk Of Cancer At Screening (PROCAS NIHR Ref: RP-PG-0707-10031) study, which recruited over 58,000 women from the Greater Manchester NHS Breast Screening Program (NHSBSP), and showed that it is possible to accurately estimate a woman's individual risk of developing breast cancer through self-report questions and information on breast density derived from mammography. PROCAS has validated an algorithm to predict risk of breast cancer in individual women and has provided 10-year risk estimates to over 54,000 women in the NHSBSP. This is the first time that personalized breast cancer risk estimates have been made available to large numbers of women from the general breast screening population.

The PROCAS study found that at least 3% of women are high risk ($\geq 8\%$ 10-year risk) when all risk factors including mammographic density are assessed and a further 10% are at moderate (5-7.9% 10-year risk) risk.

In France, the RIVIERA study (Veron et al) aimed at evaluating the feasibility of risk information delivery and personalized breast cancer surveillance planning (PSP) by community practitioners (radiologists, GPs, gynecologists). 452 women were included, 448 were evaluable. 434 accepted the personalized prevention consultation (97% acceptance). 38% of women at baseline and 25% at 48H00 had no idea of their own breast cancer risk. Most women over-evaluated their risk. At 48H00, although the median estimated lifetime risk decreased from 40 [20-50] to 30% [10-50], self-evaluation of BC risk remained rather inaccurate. Though, women were satisfied with the clarity of the information delivered regarding risk and personalized programming. Anxiety levels were limited. The only predictive factor of state anxiety at H48 was trait anxiety ($p < .0001$). No factor independently predicted for inadequate risk evaluation at baseline, while perceived clarity of information received predicted for adequate risk self-evaluation at 48H00 ($p = 0.02$). Physician's category and state anxiety both predicted for patients' satisfaction ($p = 0.02$ and 0.008 respectively). In conclusion, risk assessment and PSP delivery is feasible in community practices with high acceptance rate. The use of a dedicated tool may catch underestimated high-risk situations in up to one third of the population. Most women estimate their own breast risk inadequately, even after a dedicated education consultation.

1.1.13 Breast cancer stage 2 and higher (2+) as a surrogate end-point of breast cancer specific survival and over

Tumor stage remains of high prognostic impact in patients with early breast cancer, both at short and long term. As an illustration, in the recent, very large, European breast cancer clinical trial Mindact (Cardoso et al 2016) in which four of the 5 MyPeBS countries participated, T stage remained one of the two major prognostic factors, with a hazard ratio (HR) of 1.92 for distant metastasis-free survival at 5-years (the other one being genomic risk assessment, HR 2.41). Tumor stage is of major impact at short term for ER-negative breast cancer (HR, in which metastatic risk is almost limited to the initial 5-6 years from diagnosis). Tumor stage is however, also associated with a major long-term prognostic impact in ER+ breast cancer patients. In the 20-year analysis of ER-positive breast cancer patients included in the major randomized trials (Pan et al 2017), T stage remains a major prognostic factor at long term: T1 tumors are associated with long-lasting annual risks around 1%, while it is around 1.5% for T2, and much higher for T3 and 4. Nodal status retains the most important prognostic impact. Overall, the HR of distant metastases for stage 1 as compared to T2N0 is 0.49 years 0-5 versus 0.70 years 5-20; but stages T1N1-3 to T2N4-9 (all stage 2 and higher) are associated with a HR of long-term relapse between 1.19 and 2.63 as compared to T2N0.

1.1.14 Justification of the trial design and organization, potential biases and their prevention

Non-inferiority as primary objective

We have chosen non-inferiority as a primary objective since we wish primarily not to cause harm: it is essential, in a situation where mammographic screening as conducted in current screening programs, has demonstrated a 20% breast cancer specific mortality reduction, to make sure this aspect is preserved.

Non inferiority trials are currently largely used in case a given intervention is recognized as efficient but is associated with important toxicities, and one wants to demonstrated that a new alternative intervention is at least as efficient, but generally associated with a decrease of toxicities. Many such practice changes trials are published every year. This is the case in MyPeBS, where the current screening policy has proven to be efficient but is nowadays considered as associated with potential harms, such as false positive findings, overdiagnoses, overtreatments, radio-induced cancer. MyPeBS will de-escalate the current screening in part of the population, it is therefore crucial to demonstrate that this new screening method is primarily non-inferior to the current one.

Superiority as main secondary objective

MyPeBS will de-escalate screening in part of the population but escalate it in a large other part. There are major chances this risk-based policy may be superior to the current standard. Testing superiority of risk-based screening over standard screening is therefore the main secondary objective and MyPeBS has been designed to allow this key secondary comparison (only if non-inferiority is reached).

Stratification factors

We have carefully scrutinized all potential stratification factors, given the potential heterogeneity of the participants accrued according to the countries, as well as some heterogeneity in standard screening practices. We have finally identified 3 stratification factors that should allow an excellent balance between both arms: age (women aged <50 vs ≥ 50 , given this is the main criterion for entry into screening programs), prior mammogram (given the high rate of prevalent cancers on the first mammogram ever), and country. Stratification is not per region or center given the relative national homogeneity in practices together with the important number of centers.

Study entry mammograms

There will be no study entry mammograms. Upon enrolling in the trial and receiving a screening recommendation, each woman's next future mammogram will be scheduled. This will be dated from the date of her most recent mammogram in the two years prior to enrollment into the trial. For example, a woman who had a mammogram 3 months prior to study entry and received an annual screening recommendation would be invited to screen again 9 months after enrollment into the study. A woman who had a mammogram the year prior to study entry who receives a bi-annual screening recommendation would be invited to screen again one year after enrollment into the study.

Women who have not received a mammogram in the two years prior to enrollment may receive a mammogram at study entry if this is standard in their allocated arm and risk level (for risk-based arm).

For women assigned to the risk based screening arm who are less than 50 years of age and had no prior mammogram, the risk score will be evaluated based on the BIRADS density of D (Extremely Dense). If this assumption elevates her risk and results in a more intensive screening recommendation as compared with assuming the lowest BIRADS density, she will receive a study entry mammogram to accurately assess her risk and provide an appropriate screening recommendation. Otherwise, women who receive a screening recommendation of "No repeat screening until age 50", will not receive a study entry mammogram and will not be scheduled to receive a study mammogram until their exit mammogram unless their screening recommendation changes during the course of the study.

End of study mammogram

A study exit mammogram will be planned ONLY for the following women:

- Women in the risk-based screening arm who have been categorized as low risk (no planned mammogram during the course of the study);
- Women in the standard screening arm who had no screening mammogram during the 4-year study period given their age.

All these women will have a mandatory end-of-study mammogram at 4 years

For all the other women, the last mammography scheduled during the 4-year follow-up will be considered as the end-of-study mammography.

Organization within specific regions in the participating countries

This trial uses the existing national/regional screening structures for potential participants' information, accrual, data retrieval and follow-up. This is crucial for organizational reasons, in order not to disrupt existing pathways;

but also for future developments: risk-based screening, validated, would need to be organized within the existing structures.

Potential biases and their prevention

The identification of risk levels in the risk-based arm may induce different health behaviors that may by themselves influence the trial's result.

However, the impact of a change of health behavior on the risk of breast cancer at 4 years is expected to be null or very low. It might be impactful at a longer term. Therefore, the probability that it has an impact on the primary end point is very low but it may slightly influence some of the secondary endpoints.

Therefore, health prevention intervention will be displayed to all participants the same way.

As well a risk could be that low risk women are less breast aware. Breast awareness will therefore be displayed in all groups the same way. Regular reminders and annual risk reassessment will participate to sustain this. These measures shall contribute to both avoid study biases and risks for all participants.

1.1.15 MyPeBS population's anticipated age and risk structure

To make this trial feasible, the screening potential of each participating region/area has been carefully evaluated. Target accruals have been defined together. The recruitment will be competitive.

The realistic target age structure of women accrued in MyPeBS is: 25% aged 40-49, 45% aged 50-59, 30% aged 60-69. This age structure, as well as the risk structure in the risk-based arm, will be carefully and regularly scrutinized on order to allow potential recruitment adaptations. Monthly trial updates and steering committee meetings will be organized to allow this.

If the age and risk structure differs significantly from of initial plan, the study statistician, with the Clinical trial Steering Committee, together with the advice of the Ethics and data Monitoring Committee, will model these changes' effects on the initial statistical hypotheses and potentially propose an amendment of the study.

MyPeBS		women aged 40-49 (25%)	women aged 50-59 (45%)	women aged 60+ (30%)
risk level	average risk in level	Expected distribution	Expected distribution	Expected distribution
Low	0,8%	60%	28%	15%
average	1.4%	25%	33%	30%
high	2.3%	15%	40%	55%
TOTAL		10 625	19 125	12 750

1.1.16 Evaluation of potential screening harms in MyPeBS

Several secondary endpoints will carefully evaluate potential screening harms (safety endpoint) in MyPeBS: they include false positive recalls, negative impacts on patients reported outcomes, as well as an estimation of overdiagnosis. Finally, we will also attempt to evaluate radiation-associated risks in both arms.

Some of these evaluations will use the MISCAN model, which has been largely used for this purpose and in the context of the evaluation of large European screening programs beyond breast cancer (Van den Broek 2018; <https://www.ncbi.nlm.nih.gov/pubmed/?term=de+koning+miscan>). With the calibrated MISCAN model, the effects, risks and costs of a 30-years screening period are predicted. The main effect measures are the number of prevented breast cancer deaths and (quality adjusted) life-years gained by screening. We will also predict the number of screening examinations needed to prevent 1 breast cancer death and gain 1 life-year, and the reduction in advanced disease as a consequence of screening. Predicted risks are the number of over-diagnosed and over-treated breast cancers and the number of false-negative screening tests. False

positive screening tests will also be accounted for. Quality adjusted life years gained is calculated by applying a quality of life value to each phase of the disease. Such values have been calculated for screening attendance, the diagnostic phase, initial treatment, palliative treatment, the first year after treatment, the disease-free period >1 year after treatment, and terminal illness. By multiplying these values by the average duration of the different phases and the number of women to be expected in these phases, quality adjusted life-years are calculated. Quality adjusted life years *gained* are then calculated by comparing the predicted number of quality adjusted life years in a screening situation with the predicted number of quality adjusted life years in a no-screening situation. In this project, we intend to also use empirical data from the trial itself, by adding 5Q-ED.

Number of over-diagnosed and over-treated breast cancers: The predicted number of over-diagnosed breast cancers is calculated as the number of breast cancers that are diagnosed during the lifespan of the simulated population in a screening situation minus the numbers of breast cancers that are diagnosed during the lifespan of the population in a no-screening situation. Over-treatment is the treatment of over-diagnosed breast cancer. It is calculated as the number of over-diagnosed tumors multiplied by the probability that a certain treatment is used for that tumor. A distinction is made between tumor stages. The probabilities that a specific treatment is used for a certain screen-detected tumour stage are based on earlier estimates, and the empirical data from the trial.

Radiation risk: We estimate radiation-induced breast cancer incidence by using the excess absolute risk model from pooled analysis of 4 cohorts by Preston and colleagues, the preferred model for estimating radiation induced breast cancer incidence. This model assumes that excess risk for radiation-induced breast cancer increases linearly with increasing radiation dose within the exposure ranges from mammography. In addition, risk decreases with increasing age at exposure, especially after 50 years old (a surrogate for menopause), and increases with attained age; the highest incidence of radiation-induced breast cancer occurs late in life. We have earlier modeled the latency period for developing radiation-induced breast cancer by using a logistic function that phases in increased breast cancer risk between 4 and 11 years after exposure. We estimated radiation-induced breast cancer mortality by multiplying radiation-induced breast cancer incidence by the age-specific case–fatality rates of non–radiation induced breast cancer derived from MISCAN-Fadia and assuming 100% adherence to screening and available treatment. We assume that breast cancer induced by radiation is screen-detected at the same rate as non-induced cancer (Miglioretti, 2016).

1.1.17 Imaging techniques in MyPeBS

Breast cancer screening is based on imaging. To date, 2D mammography, either film screen or digital, has been the only available test for women at population risk. In the last five years several studies have shown that digital Breast Tomosynthesis (DBT), a 3D imaging technique, is more sensitive than full field digital mammography (FFDM) and more specific but whether or not this will result in earlier diagnosis and better prognosis is still unclear. Nevertheless, DBT used in addition to FFDM or with a synthetic 2D reconstruction from the tomo planes, received Food and Drug Administration (FDA) approval for primary screening.

Ultrasonography (US) is used as a supplement to FFDM for women with Breast density C and D according to BI-RADS classification in some countries (for example in France and Belgium in MyPeBS) and in an opportunistic manner for screening in many European countries. For women with established familial risk many guidelines (eg NICE) recommend the use of magnetic resonance (MRI) for women under 60 years.

The imminent adoption of new screening imaging technologies such as DBT and supplementary US has been carefully considered in the MyPeBS trial design. DBT is likely to be included in future screening guidelines for all or for some groups of women. Including DBT as part of the intervention, i.e. offered only to some risk groups, would make the intervention obsolete if DBT becomes standard practice. Furthermore, it would be impossible to disentangle the effect of personalizing screening and the effect of tomosynthesis improved sensitivity in the experimental arm. However it is important to show if the effect of personalized screening is similar with FFDM and DBT. Some participating centers are already using DBT with FFDM in population-based pragmatic trials or demonstration projects, thus it will be possible to have some women recruited in the MyPeBS screened with

DBT in both arms. The analysis of the trial results will be then stratified by use of DBT, and if there is no interaction, the conclusions about the effect of tailoring would be applicable to screening with FFDM and also DBT.

A specific secondary objective is therefore dedicated to evaluating the impact of DBT in MyPeBS.

The second important point in the trial design is the use of supplementary whole breast US (hand held HH or Automated Breast AB) with FFDM in women with dense breasts. In some countries screening is already modified according to breast density. Besides increasing the risk of cancer, breast density reduces mammographic sensitivity and can delay diagnosis. However pragmatically US (HHUS or ABUS) in all dense breasts would be unsustainable for most organized screenings of the participating countries.

Therefore the trial design takes into account the following constraints: 1) maintaining the control arm as the “standard of care in each country”; 2) harmonizing the experimental arm imaging procedures among countries as much as possible; 3) proposing, for high-risk women, an intervention that improves sensitivity in dense breasts; 4) proposing a sustainable protocol for personalized screening. In those centers where US is not routinely used in dense breasts, US will be added in the experimental arm only, for women who have BIRADS C/D dense breast (or equivalent with density assessment tools) and are in risk group 2/3. Optimization of the threshold for use of US will be possible according to the results of the ongoing studies, in particular the ASSURE study (conducted by centers that are included in MyPeBS) and the Wisdom trial, the USA companion study of MyPeBS.

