European recommendations are expected to clarify the position of DBT in breast cancer screening. Meanwhile, some countries and/or regions or centers, are on the process of making DBT a potential/obligate technique of breast cancer screening. DBT's position will be evolving throughout the conduct of MyPeBS trial. For these reasons, our trial allows DBT; it will very carefully assess and watch DBT use, will organize towards evaluating DBT's efficiency within the trial; but randomization will not include the use of DBT as a stratification factor.

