8.1 Statistical hypothesis and sample size determination

Randomization

Women who have signed the informed consent will be assigned a unique participant identifier and will be randomized 1:1 to either standard screening or the risk-based screening strategy. Randomization will be performed through an automated real-time online system (permutation blocks).

Stratification

Randomization will be stratified by country, age (women aged <50 vs ≥ 50), and prior mammogram (yes or no). This will ensure to balance screening modalities, global population risks, and the rate of prevalent breast cancers at entry.

Required number of women to be included

The incidence rate of stage 2 + breast cancer in the MyPeBS standard arm is expected to be around 120 cases/100,000/year. This number is derived from what is observed in the screened populations of European countries and including women aged 40 to 50 years for whom the incidence rate is lower:

- Incidence in women aged 50-74 years old is 140 cases/100,000 women/year on average in screened populations taking into account interval cancers and cancers not detected in women who are not screened
- We expect to include 25% of women aged between 40-49 years old
- Incidence in women aged 40-49 years old is half than older women
- Expected incidence of stage 2+ breast cancers for 100,000 women followed up for 1-year in the standard arm of MyPeBS is therefore: $(140 \times 0.75) + (0.25 \times 0.5 \times 140) = 105 + 17.5 = 122$. A slightly conservative estimate is therefore 120.

We anticipate a drop-out rate lower than 5% in both arms, and non-compliance rates of 10% in the risk-based screening arm and of 30% in the standard arm. These women will not be included in the per-protocol analysis due to non-compliance, in the 4-year period after inclusion.

The primary hypothesis is that the risk-based screening arm will be non-inferior to the standard screening arm in terms of cumulative hazard rate in the per-protocol population. The cumulative hazard functions of cancers of stage 2 + will be compared between the 2 study arms.

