Further assumptions are a non-inferiority margin of a 25% relative increase in the risk-based arm (null hypothesis $H_0: \lambda_e/\lambda_c \geq 1.25$ with t and c standing for experimental and standard arm, respectively; it corresponds to an absolute increase in the cumulative hazard rate of stage 2 cancer or higher after 4 years up to 120/100000 stage 2 cancers the risk-based arm under H_0), 80% power, 2.5% significance level, 1-sided test. If we assume that under the alternative hypothesis a 10% relative improvement can be expected by the experimental risk-based-stratified screening arm (i.e. $\lambda_e/\lambda_c = 0.9$) due to our anticipated increase in the average numbers of mammograms in the experimental arm, a total of 298 stage 2 breast cancers are required for the non-inferiority assessment using a logrank test. We assume a total of 85,000 participants, 42,500 in each arm, to be included over 2.5 years.

For the primary and key secondary endpoint analysis, each subject will be followed for four years, to be able to compare cycles of mammograms between the 2 screening arms. Later updates of the trial analyses will be performed using longer follow-up.

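### Section 1.1.17 would carry the trial's conclusion over to tomosynthesis if no interaction is found, which treats a low-powered, non-significant test as evidence of similarity

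*Protocol*

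**What the plan says.** Section 1.1.17 calls it important to show whether personalised screening has a similar effect with FFDM and with DBT. It notes that some participating centres already use DBT, so that some women in both arms will be screened with it. It commits to an analysis stratified by DBT use and adds that "if there is no interaction, the conclusions about the effect of tailoring would be applicable to screening with FFDM and also DBT". No other condition is attached: no margin, no confidence bound and no minimum amount of DBT information.

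Section 1.1.18 expects the place of DBT to change during the trial and says that "randomization will not include the use of DBT as a stratification factor".

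Section 8.1 sizes the trial for the overall comparison only. It uses a "non-inferiority margin of a 25% relative increase in the risk-based arm" with "80% power, 2.5% significance level, 1-sided test", states that "under the alternative hypothesis a 10% relative improvement can be expected", and concludes that "a total of 298 stage 2 breast cancers are required for the non-inferiority assessment using a logrank test".

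The DBT secondary endpoint in section 3.2.2 compares detection of stage 2+ cancer with and without tomosynthesis. It does not compare the two randomised arms within DBT.

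**The concern.** For its primary claim the protocol does not accept the absence of a detected difference. It requires a 25% relative increase to be excluded. For DBT the stated condition is weaker: the conclusion carries over unless an interaction shows up. A non-significant interaction can mean that the effects are alike, or that there were too few events to tell. The condition does not separate the two, and the fewer the DBT events, the more easily it is met.

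Section 1.1.17 itself expects DBT to enter future screening guidelines, so whether the result holds under DBT bears on how it will be used. The risk-based arm reduces imaging for low-risk women aged 50 and over, so extending non-inferiority too readily is the kind of error that the design sets out to avoid (section 1.1.14).

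**Working it through.** **Inputs from the protocol (section 8.1).** Margin 1.25; planning hazard ratio (HR) 0.90; one-sided 2.5%; 80% power; 298 events. The control rate "is expected to be around 120 cases/100,000/year", which is 0.0048 over 4 years. "We assume a total of 85,000 participants, 42,500 in each arm".

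**Assumptions not in the protocol.** True HR 0.90 with FFDM (the planning value) and 1.25 with DBT (the margin); interaction tested two-sided at 5%; a share f of events in the DBT stratum of 10% to 50%; 1:1 allocation within strata.

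**1. The plan's own figure.** ln(1.25/0.90) = 0.3285.
- Schoenfeld: 4 × (1.96 + 0.84)² / 0.3285² = 291 events.
- Freedman, with ratio 0.90/1.25 = 0.72: (1.96 + 0.84)² × (1.72/0.28)² = 297 events.

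The stated 298 is reproduced.

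**2. Range of event counts.** All randomised women, no drop-out: 42,500 × 0.0048 × (1 + 0.9) = 388. With the protocol's 10% and 30% non-compliance removed, the per-protocol count is 42,500 × 0.0048 × (0.70 + 0.90 × 0.9) = 308. So 298 is close to what the primary population would supply, and 388 is favourable to the plan.

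**3. Miss rate of the interaction test.** With E events, the standard error of the log ratio of HRs is SE = √[4/(E·f) + 4/(E·(1−f))]. The miss rate is 1 − [Φ(0.3285/SE − 1.96) + Φ(−0.3285/SE − 1.96)]. For example, at E = 298 and f = 0.3, SE = 0.253 and the miss rate is 74.5%.

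**4. Probability of a wrong extension.** This needs overall non-inferiority and no significant interaction together. The overall log HR is approximately f·ln 1.25 + (1−f)·ln 0.90, with standard error 2/√E. The probability of concluding non-inferiority is then Φ[(1−f) × 0.3285/(2/√E) − 1.96]. In this approximation the overall estimate and the interaction contrast are uncorrelated (their covariance is 4/E − 4/E = 0), so the two probabilities multiply.

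| DBT share | Interaction missed, 298 / 388 events | Overall non-inferiority concluded | Both |
|---|---|---|---|
| 10% | 86% / 84% | 72% / 83% | 62% / 69% |
| 20% | 79% / 75% | 62% / 74% | 49% / 55% |
| 30% | 74% / 68% | 51% / 62% | 38% / 42% |
| 50% | 71% / 63% | 29% / 37% | 21% / 23% |

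**5. Sensitivity of the miss rate (10–50% share, 298–388 events).**
- Interaction tested at 10%: 51–78%.
- FFDM HR of 1.0 instead of 0.90, at 5%: 80–91%.
- DBT HR of 1.5, at 5%: 29–74%, falling below half only at shares of about 20% or more.

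**6. Events for 80% power on this interaction.** (1.96 + 0.84)² / [f(1−f)] × 4/0.3285² gives about 1,164 at a 50% share and about 3,233 at 10%.

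**The case against.** The strongest objection is that the miss rate of the interaction test is not the risk that matters. A reader might infer that this trial has a 63–86% chance of wrongly extending its claim to DBT. It does not. Extension also requires overall non-inferiority, and if DBT is common and the effect is lost there, the primary test usually fails. At a 50% share the joint probability is 21–23%, about a third of the 63–71% miss rate. This stands, and the joint figures are the ones to use.

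A reader might also infer that only a minority of centres will use DBT, so that low power is certain. Section 1.1.17 says that some centres already use it, and section 1.1.18 expects use to evolve. The share is unknown, hence the range. Nor does anything in the protocol suggest that tailoring fails under DBT; the 1.25 is a test case, not a prediction.

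The sentence sits in the rationale, section 8 contains no DBT decision rule, and the level of the test may be set in a statistical analysis plan that is not shown. DBT women are also in the primary analysis, so the overall result already describes a mix of techniques. These points lower the weight of the concern. They do not remove it, because the condition is stated in advance, it is the only one given, and no analysis plan can add events.

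Finally, requiring the DBT stratum alone to meet the margin would be severe. Even at a true DBT HR of 0.90, it would fail in about 37–86% of trials over the same range of shares and events. That argues for exploratory wording rather than a second formal hurdle.

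**Conclusion.** The concern holds as a point about inference. Section 1.1.17 lets a non-significant interaction stand as evidence that tailoring works alike under FFDM and DBT, and the trial has little power to detect a relevant difference. Under the stated assumptions the probability of a wrong extension runs from about 62–69% when a tenth of events are in the DBT stratum to 21–23% when half are. The problem is therefore largest when DBT events are few. These figures are conditional on the HR pair, the 5% test and the DBT share, none of which the protocol fixes.

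The finding does not show that the result will fail under DBT. It also does not touch the 298-event calculation, the decision not to stratify randomisation by DBT, or the primary and key secondary analyses.

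**What to change.** In section 1.1.17, replace the no-interaction condition with a statement along these lines:
- The HR in each DBT stratum and the ratio of the two HRs will be reported with 95% confidence intervals.
- A non-significant interaction will not be taken as evidence that the effects are alike.
- Applicability to DBT will be judged from the DBT-stratum HR and its interval read against 1.25. It will be described as exploratory, or as not established where the interval does not exclude 1.25.

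This is a change of wording and needs no extra data. The cost is a less firm statement about DBT in many outcomes. For example, with 30% of 298 events in the stratum (about 89) and an observed HR of 0.90, the upper limit is 0.90 × exp(1.96 × 2/√89.4) = 1.36, which does not exclude the margin.
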